13.1.2. Determination of Sample Size

The following assumptions were used in sample size calculations:

- Exponential survival curves, placebo survival estimate of 0.5 at 8 years with a hazard ratio of 0.60, and total study duration of 8 years, allowing for 2 years accrual and 6 years of follow up.
- Subjects will be randomized in a 1:1 ratio to placebo or OCA.
- The 2 groups will be compared using a 2-sided log rank test at the 5% level of significance.

Based on the randomization ratio, significance level, and assumed hazard ratio, a total of 121 events (both groups combined) will provide 80% power to demonstrate a statistically significant difference between OCA and placebo on time to liver-related outcomes, including all-cause mortality.

In addition, based on the remaining assumptions stated above, it is estimated that approximately 350 subjects will be enrolled to attain 121 events.

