13.1.9. Alternative Primary Analysis

Based on sample size re-estimations, it may be determined that subjects will be enrolled to receive open-label OCA from that point forward, and the new primary efficacy analysis will become the comparison of all subjects in OCA population, to all control subjects (randomized placebo and historical controls) on time to liver transplant or death (all-cause) (see [Section 13.1.2.1](#)). Similar statistical methodology as specified above in [Section 13.1.8](#) for supportive analyses will be utilized.

The propensity score quintile will be then be used as the stratification factor in the stratified log rank test to compare groups. KM estimates of the distribution of the time-to-event will be tabulated and graphed by treatment group. The tabulation will include the KM estimate of the medians and corresponding 95% CIs if the medians can be estimated. The number and percent of subjects censored and with events will be presented. The hazard ratio and 95% CI will be determined based on a Cox regression model stratified by randomization strata to estimate the magnitude of the effect.

In addition, the outcome events specified above in Section 13.1.8 will also be evaluated to compare all subjects in OCA population to all control subjects (randomized placebo and historical controls).

Sensitivity analyses will be conducted limiting to the separate individual historical control databases, ie, UK-PBC Group and Global PBC Study Group. To evaluate the robustness of the propensity score estimations, additional algorithms and factors may be considered.

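### Historical-control comparisons in 13.1.8 and 13.1.9: the test is stratified by propensity quintile, but the hazard ratio and CI by randomization strata only

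*Protocol*

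**What the plan says.** Section 13.1.9 applies if later subjects are enrolled to open-label OCA. The primary comparison then becomes all OCA subjects against randomized placebo plus historical controls, on time to liver transplant or all-cause death. For the test it says: "The propensity score quintile will be then be used as the stratification factor in the stratified log rank test to compare groups". For the effect size it says: "The hazard ratio and 95% CI will be determined based on a Cox regression model stratified by randomization strata".

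Section 13.1.8 has the same structure for randomized OCA subjects against registry controls on six outcomes: all-cause death, liver-related death, transplant, transplant or all-cause death, transplant or liver-related death, and hepatocellular carcinoma. Its test uses propensity quintiles and its Cox model uses randomization strata, in the same words.

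Three other places bear on the point:
- Section 9.4 defines the randomization strata as UDCA treatment (yes/no) and mean baseline bilirubin (above ULN, or at or below it).
- Section 13.1.8 explains that matching must take in the full range of covariates on which treated subjects and historical controls might differ, if it is to mitigate bias.
- Section 13.1.3 uses the same Cox sentence for the randomized comparison, where it is appropriate.

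**The concern.** A stratified log-rank test and a stratified Cox model are normally a matched pair: the log-rank statistic is the score test from the Cox model with the same strata. Here the strata differ, so the p-value and the hazard ratio beside it refer to differently adjusted comparisons.

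In 13.1.3 randomization balances everything else, so stratifying on the randomization factors is enough. Against registry controls nothing is balanced by design, and the propensity score is the protocol's only stated means of balancing. The Cox model as specified does not use it.

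At stake are the reported size of benefit and its CI for the supportive outcomes and, if the switch in 13.1.2.1 is triggered, for the primary result. A reader could see a non-significant adjusted test next to a CI that excludes 1, or the reverse.

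**Working it through.** **1. The plan's own figure.** The only design calculation is for the randomized comparison in 13.1.2. Inputs: "The 2 groups will be compared using a 2-sided log rank test at the 5% level of significance"; "placebo survival estimate of 0.5 at 8 years with a hazard ratio of 0.60"; "Subjects will be randomized in a 1:1 ratio to placebo or OCA"; "a total of 121 events (both groups combined) will provide 80% power". Schoenfeld's formula gives

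d = 4(z₀.₉₇₅ + z₀.₈₀)² / (ln 0.60)² = 4(1.960 + 0.842)² / (0.511)² = 120.3, rounded up to 121.

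Power at 121 events is 80.2%. The figure reproduces and does not depend on this point. The protocol gives no calculation for the historical-control comparisons.

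**2. The sections side by side.**

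| Section | Comparison | Log-rank strata | Cox strata |
|---|---|---|---|
| 13.1.3 | randomized OCA v randomized placebo | randomization factor | randomization strata |
| 13.1.8 | randomized OCA v registry controls | propensity quintile | randomization strata |
| 13.1.9 | all OCA v placebo plus registry controls | propensity quintile | randomization strata |

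The strata match in the first row only. No section specifies a propensity-adjusted hazard ratio. The closing remark in 13.1.8 and 13.1.9 about additional algorithms and factors concerns how the propensity score is estimated. The single-database sensitivity analyses name no other Cox model.

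**3. What the difference can do.** The protocol gives no covariate imbalance, so any size rests on assumption. Two illustrative simulations, both with a true hazard ratio of 1.0 and 175 OCA subjects (half of 350):

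*A.* 600 to 3,000 controls; one prognostic index with hazard ratio 2 per SD; a 1-SD imbalance; stratification on one dichotomy against propensity quintiles; 150 replicates per scenario.

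*B.* 2,000 controls; three prognostic covariates outside UDCA and bilirubin, shifted 0.2, 0.3 or 0.3 SD in favour of trial subjects, with log-hazard 0.2, 0.35 or 0.5 per SD respectively; UDCA and bilirubin distributed alike in both groups; 300 runs each.

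| Mean hazard ratio (truth 1.0) | Crude | Randomization-type strata | Propensity quintiles |
|---|---|---|---|
| A, OCA healthier | 0.52–0.55 | 0.76–0.79 | 0.92–0.94 |
| A, OCA sicker | 1.9 | 1.41 | 1.12–1.17 |
| B, three settings | 0.88 / 0.75 / 0.69 | 0.88 / 0.74 / 0.69 | 0.98 / 0.96 / 0.96 |

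In B the 95% CI excluded 1 in 14%, 59% and 81% of runs with randomization strata, and in about 4% with quintiles.

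**4. Share of the crude bias left, on the log scale (A).**
- Healthier, dichotomy: ln 0.76 / ln 0.52 = 0.274 / 0.654 = 42%; ln 0.79 / ln 0.55 = 0.236 / 0.598 = 39%. About 40%.
- Sicker, dichotomy: ln 1.41 / ln 1.9 = 0.344 / 0.642 = 54%.
- Quintiles: ln 0.92 / ln 0.52 = 13% and ln 0.94 / ln 0.55 = 10% (healthier); ln 1.12 / ln 1.9 = 18% and ln 1.17 / ln 1.9 = 24% (sicker).

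In B essentially all of the crude bias remains under randomization strata. That follows from the set-up, because every confounder lies outside the two strata.

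**The case against.** **The test is sound.** In both sections the significance decision comes from the propensity-stratified log-rank test. A reader might infer that a false claim of efficacy could follow from the Cox sentence; the protocol does not support that. This stands, and it confines the fault to the hazard ratio and CI.

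**The scope is limited.** The planned primary analysis in 13.1.3 is untouched. The 13.1.8 comparisons are supportive and lie outside the testing hierarchy of 13.1.11. Section 13.1.9 applies only if, after 4 years of accrual, at least 2 more are needed, and 13.1.2.1 requires an amendment for changes to treatment allocation. This stands too.

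**The model can probably be fitted.** A reader might infer that it cannot, because registry controls have no randomization stratum. But 13.1.1.1 says the databases hold baseline characteristics and longitudinal liver biochemistry, and 13.1.8 names UDCA among the covariates collected. Both factors look derivable, although no derivation is described. The fault is therefore inadequate adjustment.

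**The bias may be modest.** Controls are to meet the same eligibility criteria where possible (13.1.1.1) and to have demonstrated comparability (13.1.1). Neither simulation models that restriction, and A uses one dichotomy where the protocol has two factors. It would be tempting to say that most of the confounding remains. Simulation A leaves about 40% or 54% of the crude bias and B nearly all of it, so the share depends on the assumptions.

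**What does not stand** is leaving the matter to the SAP, which is not at hand. The protocol defers the list of covariates to it, but fixes the Cox stratification itself.

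**Conclusion.** The Cox sentence in 13.1.8 and 13.1.9 is wrong for the comparison it serves. It stratifies the effect estimate on two dichotomies, while the test uses the propensity score and the section's own rationale calls for a full range of covariates. The hazard ratio and CI would be less well adjusted than the test and could disagree with it. This affects the six supportive outcomes in any case, and the primary effect size only if the open-label switch occurs.

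The residual bias cannot be determined from the protocol. On the assumed inputs above, with no true effect, the hazard ratio was about 0.69 to 0.88 (OCA healthier) or about 1.41 (OCA sicker) with randomization-type strata, against 0.92 to 0.98 or 1.12 to 1.17 with quintiles. These figures illustrate the mechanism and do not forecast the trial's result.

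The wording matches 13.1.3, and a reader might conclude that it was copied from there. The protocol does not say how it arose, and the point does not depend on it.

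**What to change.** In the Cox sentence of 13.1.8 and of 13.1.9, name the propensity score quintile as the stratification factor in place of the randomization strata, so that the estimate matches the log-rank test. Change nothing else. The randomized comparisons in 13.1.3 to 13.1.5 and the responder Cochran–Mantel–Haenszel test in 13.1.6.1 are rightly stratified by the randomization factor.

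The cost is one phrase in two sections. The 121 events and about 350 subjects stay as they are. The change should be made before the propensity score is determined and treatment is unblinded.

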13.1.10. Handling of Dropouts or Missing Data

Subjects who discontinue investigational product are expected to continue in the study until study termination.

Missing data will be assumed to be missing at random. In order to determine the effect of missing data on the analysis, efficacy endpoints will be analyzed using different methods of imputation as described below.

13.1.10.1. Time to Event Endpoints

For the time to event analyses, subjects who do not experience an event will be censored at the time of their last contact. Subjects with no data after randomization will be considered to have an event on Day 1 (first day of investigational product dosing).

For analyses of the percentage of subjects with an event, subjects with no data after randomization will be considered to have an event.

All time to event endpoints include only adjudicated events. Sensitivity analyses may consider all events regardless of adjudication. Events with discrepant adjudication will be analyzed using both results.

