8.4.2. Other Reasons for Discontinuation of Study or Investigational Product

Subjects that discontinue investigational product are expected to continue in the study until the end of the study, and the study will only terminate at the time when the needed number of adjudicated events has accrued or at the discretion of the Sponsor. If a subject reaches an event, he or she should continue the regular visit schedule and continue taking investigational product as long as the Investigator assesses it as safe. Subjects who choose to discontinue investigational product prior to termination of the study need to also continue to follow the regular visit schedule

through to study closure. In general, subjects should be strongly encouraged to both stay on investigational product and remain in the study until study termination. Early termination procedures should only be conducted if the subject withdraws consent (See [Section 9.7.18](#) Early Discontinuation and/or Early Termination Procedures).

The following events are considered appropriate reasons for a subject to discontinue investigational product; however, these subjects are expected to continue in the study until study termination and the study will only terminate at the time when the needed number of adjudicated events has accrued (or at the discretion of the Sponsor):

- Subject begins treatment with commercially available OCA
- The Investigator or Sponsor considers that it is advisable or in the best interest of the subject.
- The occurrence of clinical or laboratory AEs considered by the Investigator to be clinically important safety concerns and related to study drug.
- Withdrawal of consent
 - Consent may be fully withdrawn (in which case the subject discontinues both investigational product and study visits and procedures).
 - Consent may be modified to discontinue study visits but allow semi-annual telephone contact.
 - Consent may be modified to discontinue study visits or semi-annual telephone contact but allow continued access to medical records to assess for potential adjudicated hepatic and/or cardiovascular events.

Subjects who undergo a liver transplant during the course of the study must discontinue investigational product and discontinue the study visit schedule. However, these subjects should be encouraged to consent to the semiannual telephone contact and/or continued record review only to allow for secondary outcome events data to be collected.

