Early Termination	Discontinued	Withdrawn	No additional visits except EOT/EOS	Combined Visit, Completed as close as possible to last dose IP	
Treatment Discontinuation^b	Discontinued	Active	Regular Visit Schedule	Complete as close as possible to last dose IP	Complete at Final study visit
	Discontinued	Semiannual contact ^c	Telephone contact every 6 months (± 2 weeks)	Combined Visit, Completed as close as possible to last dose IP	
	Discontinued	Record review only ^c	Record review only	Combined visit Completed as close as possible to last dose IP	
Sponsor Termination	Discontinued	N/A	No additional visits except EOT/EOS	Combined visit Completed as close as possible to last dose IP	
Pregnancy	Interrupted	Retained	Regular Visit Schedule	Complete as close as possible to last dose IP	Complete at Final study visit
	Discontinued	Complete per the above scenarios - Early Termination or Treatment Discontinuation			
Lost to Follow-up	Discontinued	LTF	None	Unable to complete due to LTF status	

EOS = end of study; EOT = end of treatment; IP = investigational product

^a Refer to [Section 7.1.2](#) Schedule of Study Procedures, [Table 2](#) for all procedures and evaluations required at the End of Treatment and End of Study Visits.

^b Includes initiation of commercially available OCA.

^c Outcomes data to be discussed or collected include data related to adjudicated hepatic and cardiovascular event-related data. No additional data (e.g. AE, concomitant medication, etc) data will be collected, except as indicated in [Section 12.1.7](#).

Some assessments noted below may be omitted if they have been completed within the 6 months (or the timeframe otherwise specified) and so long as safety issues do not warrant repeat testing.

Prior to the EOT/EOS Visit:

If possible to do before the visit, when scheduling the EOT/EOS visit, reiterate dosing instructions and advise the subject:

- If applicable, NOT to take investigational product on the morning of the next visit, and
- To bring the investigational product bottle(s); if applicable, s/he will dose at the clinic, and

- To fast overnight (at least 8 hours) prior to the next visit. Fasting is required prior to all study visits, but water is permitted.

During the EOT/EOS Visit:

- Perform a physical examination (including smoking and alcohol consumption habits).
- Perform assessment for calculation of Mayo Risk Score.
- Perform assessments for calculation of Child-Pugh Score.

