Hematology	Hemoglobin, hematocrit, white blood count with differential, neutrophils, lymphocytes, monocytes, eosinophils, basophils, platelets, red blood cell count (including MCV, MCH, MCHC)
Coagulation	Prothrombin time (PT), partial thromboplastin time (PTT), international normalized ratio (INR)
Urinalysis	pH, specific gravity, total protein, glucose, ketones, bilirubin, blood, microscopic exam, urobilinogen, albumin, creatine, leucocytes, nitrates, albumin/creatinine ratio (if positive)
Biomarkers of Hepatic Fibrosis and/or Inflammation	IgM, C-reactive protein (CRP), TNF- α , FGF-19, CK-18, ELF, and others as determined during course of study
Measurement of Liver Fibrosis	Fibroscan
Bone Density Assessment	DEXA
Genetics	DNA including single-nucleotide polymorphisms (SNPs) that may be involved in PBC; RNA
Blood Sample for Future Analysis	PBC autoantibodies and other cytokines and interleukins TBD
Other	OCA (parent and conjugates [glyco and tauro]) and C4

The Investigator should manage subjects with clinically significant lipoprotein abnormalities using local standard of care procedures as appropriate after assessing the individual subject's total cardiovascular risk profile.

Urine-based β -hCG pregnancy tests will be performed in female subjects of childbearing potential per protocol specified visits. If a urine pregnancy test is positive, a serum pregnancy test must be performed to confirm the result. If positive, the Sponsor must be notified and the subject will be followed, as outlined in [Section 12.1.9](#) through pregnancy outcome.

MELD scores, Child-Pugh score, and MRS will be calculated at screening, and at quarterly (MELD and Child-Pugh scores) or semi-annual (MRS) visits based on serum chemistry and coagulation.

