13.1.4. Key Secondary Efficacy Analyses

The key secondary efficacy endpoints will compare OCA to placebo on the following:

- Time to first occurrence of MELD score ≥ 15
- Time to liver transplant or death (all-cause)
- Change from Baseline in total bilirubin at end of study
- Change from Baseline in ALP at end of study

The key secondary efficacy analyses will compare randomized OCA to randomized placebo in ITT population with respect to the key secondary efficacy endpoints. Only adjudicated events will be included in time-to-event analyses. The comparison (hypothesis testing) will be conducted as specified in [Section 13.1.11](#) in a sequential closed testing gate-keeping procedure, provided that the primary efficacy endpoint comparison is statistically significant in favor of the

OCA treatment group. If the primary comparison is not statistically significant then comparison of the secondary endpoints will be considered as descriptive and exploratory. This procedure controls the study-wise type I error.

The 2 treatment groups will be compared using the same methodology as specified for the primary efficacy analysis ([Section 13.1.3](#)).

Analyses of change from Baseline to end of study in ALP and total bilirubin will be compared between treatment groups using analysis of covariance (ANCOVA) with change from Baseline as the dependent variable including treatment group and randomization stratification factor as fixed effects and the Baseline values as a covariate. The same analysis will be carried out using percentage change from Baseline as the dependent variable.

Descriptive statistics of the laboratory values will be summarized by treatment group. The results, change from Baseline, and percentage change from Baseline values as well as estimates of least-square means, standard errors, and 95% CIs will be presented by treatment group. Estimates of the mean difference between treatment groups, the standard error of the difference, and 95% CI of the difference will be presented.

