13.1.11. Multiple Comparisons/Multiplicity

The key secondary efficacy endpoints are as follows:

- Time to MELD score ≥ 15
- Time to first occurrence of liver transplant or death (all-cause)
- Change from Baseline in total bilirubin at end of study
- Change from Baseline in ALP at end of study

The hypothesis testing of key secondary analyses will compare placebo and OCA and will be conducted in a sequential closed testing gate-keeping procedure (in the order in which the key secondary endpoints are stated above), provided that the primary efficacy endpoint comparison is statistically significant in favor of OCA. If the primary comparison is not statistically significant then comparison of the secondary endpoints will be considered as descriptive and exploratory. This procedure controls the study-wise type I error.

- First (step 1) placebo and OCA will be compared with respect to the primary efficacy endpoint. If the comparison achieves statistical significance at 2-sided 0.05 level in favor of OCA group, then
- The time to MELD score ≥ 15 will be compared between placebo and OCA (step 2). If the comparison achieves statistical significance at 2-sided 0.05 level in favor of OCA group, then
- The time to liver transplant or death (all-cause) will be compared between placebo and OCA (step 3). If the comparison achieves statistical significance at 2-sided 0.05 level in favor of OCA group, then
- Change from Baseline in total bilirubin will be compared between placebo and OCA (step 4). If the comparison achieves statistical significance at 2-sided 0.05 level in favor of OCA group, then
- Change from Baseline in ALP at the end of study will be compared between placebo and OCA (step 5).

If at any step defined above the comparison is not statistically significant at the 2-sided 0.05 level then the remaining comparisons in the stated hierarchy will be considered descriptive and exploratory. The study-wise type I error will be maintained with the above closed procedure.

Additional efficacy endpoints will be analyzed; however, hypothesis tests will be applied for descriptive and exploratory purposes only.

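### Censoring time to MELD ≥15 at last contact counts time without MELD measurement as MELD-free, and can bias its hazard ratio if leaving laboratory visits differs by arm

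*Protocol*

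**What the plan says.** Section 13.1.10.1 states that, in the time-to-event analyses, "subjects who do not experience an event will be censored at the time of their last contact". It makes no exception by endpoint. Section 13.1.4 lists "Time to first occurrence of MELD score ≥ 15" as the first key secondary endpoint and adds: "The 2 treatment groups will be compared using the same methodology as specified for the primary efficacy analysis". That means a stratified log-rank test, Kaplan-Meier curves and a stratified Cox model. Section 13.1.11 tests this endpoint as step 2, at the two-sided 0.05 level, once the primary is significant in favour of OCA.

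MELD is calculated at screening and then, under Section 12.2.7, "at quarterly (MELD and Child-Pugh scores) or semi-annual (MRS) visits based on serum chemistry and coagulation". Contact can continue after these measurements stop:

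- Section 8.4.2: "Subjects who undergo a liver transplant during the course of the study must discontinue investigational product and discontinue the study visit schedule". It adds that "these subjects should be encouraged to consent to the semiannual telephone contact and/or continued record review only".
- The same section lets other subjects reduce their consent to telephone contact or to record review.
- Table 7 in Section 9.7.18 gives the telephone schedule: "Telephone contact every 6 months". Its footnote limits the data in both reduced modes to hepatic and cardiovascular outcome events, apart from the SAE provision. It describes no laboratory sampling.

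**The concern.** Last contact is a sound censoring date for death and transplant, because a call or a record establishes both. It does not suit an endpoint that needs a blood test. A subject who has had no MELD ≥15 and moves to telephone follow-up stays in the risk set, recorded as event-free, until the last call. Follow-up is expected to last about 6 to 8 years, so this can be a long stretch. After a transplant, MELD also no longer describes the native liver.

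Section 13.1.10 assumes that missing data are missing at random. Under the last-contact rule unmeasured MELD is not treated as missing at all; it is counted as absence of the event.

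The endpoint carries alpha. If the date distorts the comparison, step 2 may fail and block the later steps, or may pass too easily and open them.

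**Working it through.** **1. The plan's own figure.** Section 13.1.2 gives a hazard ratio of 0.60, two-sided 5%, 80% power and 1:1 allocation. Events = 4(1.960 + 0.842)² / (ln 0.60)² = 31.40 / 0.2609 = 120.3, rounded up to 121. This reproduces the protocol. There is no corresponding figure for MELD ≥15, nor for the number of transplanted or telephone-only subjects.

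**2. Who is affected.**
- Affected: subjects with no MELD ≥15 so far who leave the visits but accept continued contact.
- Not affected: subjects who stop study drug or switch to commercial OCA (Sections 8.4.2 and 9.2.1 keep them on the visit schedule), subjects who withdraw fully, and subjects who reached MELD ≥15 before transplant.

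**3. Cumulative incidence.** Assume a placebo MELD hazard λ = ln 2 / 8 = 0.0866 per year. This is the composite rate in Section 13.1.2, so it is an upper bound for one component. Let subjects leave for telephone-only contact at rate q per year, independently of MELD risk, and let no MELD ≥15 be found afterwards.
- True 6-year incidence: 1 − exp(−6λ) = 40.5%.
- Incidence shown under last contact: λ/(λ+q) × [1 − exp(−6(λ+q))]. This is 38.4%, 35.5% and 32.9% for q = 0.02, 0.05 and 0.08.

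**4. Hazard ratio and test.** Simulation with 350 subjects, follow-up uniform over 6 to 8 years, exponential times, an unstratified log-rank test and Cox model, and 3,000 runs per row. The Monte Carlo standard error of a proportion is at most √(0.25/3000) = 0.9 points. Leaving rates are assumed. Each result is last contact / last MELD.

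| True HR | Leaving per year, placebo / OCA | Estimated HR | Significant for OCA |
|---|---|---|---|
| 0.60 | 2% / 2% | 0.604 / 0.600 | 79.1% / 79.4% |
| 0.60 | 5% / 5% | 0.607 / 0.600 | 74.2% / 77.0% |
| 0.60 | 5% / 2% | 0.672 / 0.598 | 57.6% / 79.2% |
| 0.60 | 8% / 3% | 0.719 / 0.598 | 41.0% / 75.9% |
| 0.60 | 2% / 5% | 0.542 / 0.597 | 91.7% / 79.2% |
| 1.00 | 5% / 5% | 0.996 / 0.997 | 2.7% / 2.5% |
| 1.00 | 5% / 2% | 1.112 / 0.997 | 0.5% / 3.0% |
| 1.00 | 2% / 5% | 0.899 / 1.001 | 9.5% / 2.3% |
| 1.00 | 3% / 8% | 0.840 / 0.997 | 17.3% / 2.8% |

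On the hazard ratio the driver is the difference in leaving between arms, not leaving as such.

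**5. Transplant alone.** Assume placebo hazards of 0.05 per year for MELD ≥15 and 0.02 for transplant, both with hazard ratio 0.60, and 175 subjects per arm. The last-contact rule moves the hazard ratio from 0.60 to about 0.61–0.62 and costs about 5 points of power (61% to 55% in one run, 62% to 57% in another). With no effect on MELD but hazard ratio 0.60 on transplant, false OCA wins are 1.9%, so there is no inflation.

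**The case against.** **No imbalance is documented.** The protocol gives no transplant or reduced-consent rates. With equal leaving, the hazard ratio and type I error hold. This stands, and it is why the point says that the rule can bias the result. A reader might infer that the endpoint is biased whatever happens, or that the claimed error control fails. The documents do not support either. The table also gives stand-alone test rates, and step 2 is reached only after a significant primary.

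**Some MELD values will still arrive.** Unscheduled laboratory tests are allowed (Section 9.7.19), MELD ≥15 is among the adjudicated events (Section 6.1), and record review could surface local results. This reduces the gap for record-review subjects. Telephone contact alone would not close it.

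**Kaplan-Meier and competing events.** A reader might infer that the rule overstates incidence by treating transplant and death as ignorable censoring. For transplant it does not, because transplanted subjects stay in the risk set. With hazards of 0.05 and 0.02 over 8 years, the last-contact curve gives 30.8%. The cumulative incidence is 0.05/0.07 × [1 − exp(−0.56)] = 30.6%, and censoring at transplant gives 1 − exp(−0.40) = 33.0%. For death, last contact already ends at-risk time.

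**This belongs in the SAP.** Display methods and the descriptive endpoints do, including varices and the HCC component. The censoring date does not: the protocol states it for all endpoints, and a SAP using another date for MELD would depart from that text.

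**The remedy is not neutral.** Subjects transplanted or leaving while deteriorating are plausibly close to MELD 15, so censoring them there may be informative. The simulations recover 0.60 because leaving was assumed independent of MELD risk. This stands and calls for sensitivity analyses.

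**Conclusion.** The point holds for one endpoint. As written, the rule counts time without scheduled MELD measurement as MELD-free in an alpha-controlled comparison. It understates MELD incidence among telephone-only subjects.

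The hazard ratio is materially affected only when leaving differs by arm. It is diluted if placebo subjects leave more, and shifted in favour of OCA if OCA subjects leave more. Either is conceivable: OCA is meant to reduce transplants, and pruritus, its primary related adverse event (Section 5.6), could move more OCA subjects to telephone contact. The transplant route is small and conservative. All magnitudes rest on assumed rates.

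The primary composite is largely spared, since transplant and death are events there. Its MELD component has the same gap for telephone-only subjects. A reader might infer a defect that must be repaired before the trial can be interpreted; the documents do not go that far. It is a specific, inexpensive correction that should be made before unblinding.

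**What to change.** Amend Section 13.1.10.1 as follows, and carry it into the SAP:

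- Censor time to MELD ≥15 at the last evaluable MELD assessment, counting unscheduled and record-review values submitted for adjudication.
- End at-risk time for this endpoint at transplant or death, using a cause-specific log-rank test and Cox model.
- Keep last contact as the censoring date for death and transplant.
- Add two sensitivity analyses, because the new censoring may itself be informative: a composite of MELD ≥15, transplant or death; and the primary composite censored at the last visit with a MELD.

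The cost is protocol and SAP wording, a little programming and slightly less follow-up time for this endpoint. Scheduled visits already supply their assessment dates; dates of any record-review MELD values must be kept with the adjudication material.
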